12 PROTOCOL DEVIATIONS

The details of the protocol deviation (date, reason and type of deviation) should be clearly documented in the source data. A Deviation Form should be completed to notify the Trial Office of the deviation.

Page | 22 of 64 Version 1.0a, 8 Apr 2016

13 WITHDRAWAL OF CONSENT

Patients and/ or Carers may withdraw consent at any time during the trial.

The details of withdrawal (i.e. date, reason and type of withdrawal) should be clearly documented in the source data. A Patient/Carer Withdrawal Form should be completed to notify the Trial Office of the patient's or carer's withdrawal.

13.1 Patient

Three broad categories of withdrawal of consent are defined for the patient:

- Patient would like to withdraw from the feasibility study or the RCT (as applicable), but is willing to
 be followed up according to the trial schedule for survival analysis and resource usage (i.e. the
 patient has agreed that follow-up data can be collected and used in the trial analysis)
- Patient does not wish to attend the feasibility study or the RCT follow-up visits but is willing to be
 followed up at standard clinic visits for survival analysis (i.e. the patient has agreed that follow-up
 data can be collected at standard clinic visits and used in the trial analysis)*
- Patient is not willing to be followed up for protocol defined purposes at any further visits (i.e. the
 patient has agreed that any data collected prior to the withdrawal of consent can be used in the trial
 analysis)
- * All patient data will be included in the analysis on an intent-to-treat basis.

13.2 Carer

The carer is free to stop completing the Carer Questionnaires at any time. Any data collected up until the point of withdrawal will be used in the analysis.

The withdrawal of the carer will not affect the patient's participation in the trial.

Page | 23 of 64

14 ADVERSE EVENT REPORTING

Adverse Events (AEs) are not expected in this study however the collection and reporting of AEs will be in accordance with the Research Governance Framework for Health and Social Care and the requirements of the National Research Ethics Service.

Definitions of different types of AE are listed in Appendix 11.

14.1 Reporting Requirements

14.1.1 Serious Adverse Events

Investigators should report AEs that meet the definition of an SAE (see Appendix 11) and that are thought to be attributable to the SPECIAL protocol (i.e. related) and are thought to be unexpected only. Please note the SPECIAL protocol does not determine patient treatment for their cancer and as such events linked to cancer treatment SHOULD NOT be reported as SAEs however details of all hospital admissions will be collected on the CRF to inform the health economic analysis.

14.1.2 Expected Serious Adverse Events

No SAEs are expected to occur as a result of participation in the SPECIAL trial.

14.1.3 Reporting Period

Details of all SAEs will be documented and reported from the date of entry until the six month follow up time point.

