3.2 Randomised Controlled Trial

Stage two will be a non-blinded, prospective randomised controlled interventional trial in which consenting patients with newly diagnosed stage IV NSCLC will be randomly allocated to either standard oncological/respiratory care alone, where the patient could be later referred to palliative care specialists, or early referral to local palliative care services (i.e. within two to four weeks of diagnosis) as well as local standard oncology/respiratory medical treatment and follow-up.

Patients randomised to the early SPC referral arm will be further randomised into two groups where half the patients will be asked to complete a SPARC questionnaire to assess their wider holistic needs.

Patients will be entered into the trial over a three year period and will be followed up for three years or until death.

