7.2.2 Randomised Controlled Trial Assessment Schedule

The patient visit schedule is summarised in Table 2.

Table 2: Patient Visit Schedule - Randomised Controlled Trial

Assessment		Follow-up Period	On-going Follow-up	After Death
		Monthly, or to coincide with treatment schedule for 6 months	2-monthly for 6 months then 3 monthly until death or further two years	
Eligibility check	X			
ECOG Performance Status	X	X	X	
Patient's Informed Consent	X			
Carer's Informed Consent (once patient has consented)	Х			
Modified Glasgow Prognosis Score (mGPS)	Х	X*		
Patient Randomisation	Х			
Demography, medical history	Х			
Concomitant medication	Х	Х	Х	
Scottish lung cancer co-morbidity index	Х			
Patient Questionnaire Booklet (randomisation and time-point specific)	Х	X	X	
Patient diary collected		X	X	
Sheffield Profile for Assessment and Referral for Care (SPARC) ONLY IF RANDOMISED TO ARM B2 [†]	Х	X	X	
Montreal Cognitive Assessment scale (MoCA) (consenting participants only)	Х	X *		
Carer Questionnaire Booklet	Х	X	X	
Qualitative Interviews (consenting participants only)		X [‡]		
Recording of resource use		X	X	
Treatment details and measurement of response (as per local practice)		X	X	
Relapse/Progression		X	Х	
Notification of death, location of death				Х
Clinical Records Review: Interventions and Specialists seen during month leading up to death				Х
CODE™ (consenting participating carers only; 2-3 months post-bereavement)				Х

Notes

Page | 16 of 64

^{*} mGPS & MoCA will be measured at 3 and 6 months during follow-up (see Section 7.3)

[‡] Performed at approximately 3 and 6 months from trial entry

[†] A copy of SPARC should be provided to the patient's palliative care team after each assessment, the original should be returned to the Trial Office and a copy retained in the ISF

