7.2.2.3 Long Term Follow-up Assessments

After the six month follow-up visit RCT patients will be followed up every two months for a further six months. Thereafter patients will be followed up three monthly until death or for a maximum of two years.

The patient should be asked to complete:

- SPARC questionnaire (only if randomised to Arm B2)
- Long Term Follow-up Patient Questionnaire Booklet

Page | 18 of 64 Version 1.0a, 8 Apr 2016

Please note: A copy of SPARC should be provided to the patient's palliative care team after each assessment, the original should be returned to the Trial Office and a copy retained in the ISF

Please note: A copy of SPARC should be provided to the patient's palliative care team after each assessment, the original should be returned to the Trial Office and a copy retained in the ISF

The carer should be asked to complete the Carer Questionnaire Booklet*.

Completed questionnaires should be returned to the Trial Office with the patient's completed diary sheets.

*Please note: If the trial registered carer is not accompanying the patient, please send the carer questionnaire booklet home with patient so that the carer may complete and return it to the site research team at the next follow-up clinic visit.

Survival data, including information on relapse and progression and on-going resource use will be collected on the CRF. If the patient receives additional treatment for relapse/progression they should resume monthly assessments (see Section 7.2.2.2).

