APPENDIX 11 – DEFINITION OF ADVERSE EVENTS

Adverse Event

Any untoward medical occurrence in a patient or clinical trial subject participating in the trial, which does not necessarily have a causal relationship with the treatment received.

Comment:

An AE can therefore be any unfavourable and unintended sign (including abnormal laboratory findings), symptom or disease temporally associated with the use of a medicinal product, whether or not related to the medicinal product.

Related Event

An event which resulted from the administration of any of the research procedures.

Serious Adverse Event

An untoward occurrence that:

- Results in death unrelated to the original lung cancer diagnosis and treatment
- Is life-threatening*
- Requires hospitalisation** or prolongation of existing hospitalisation
- Results in persistent or significant disability or incapacity
- Consists of a congenital anomaly/ birth defect
- Or is otherwise considered medically significant by the Investigator***

Comments:

The term severe is often used to describe the intensity (severity) of a specific event. This is not the same as serious, which is based on patients/event outcome or action criteria.

- * Life threatening in the definition of an SAE refers to an event in which the patient was at risk of death at the time of the event; it does not refer to an event that hypothetically might have caused death if it were more severe.
- **Hospitalisation is defined as an unplanned, formal inpatient admission, even if the hospitalisation is a precautionary measure for continued observation. Thus, hospitalisation for protocol treatment (e.g. line insertion), elective procedures (unless brought forward because of worsening symptoms) or for social reasons (e.g. respite care) are not regarded as an SAE.
- *** Medical judgment should be exercised in deciding whether an AE is serious in other situations. Important AEs that are not immediately life threatening or do not result in death or hospitalisation but may jeopardise the subject or may require intervention to prevent one of the other outcomes listed in the definition above, should be considered serious.

Unexpected and Related Event

An event which meets the definition of both an Unexpected Event and a Related Event.

Unexpected Event

The type of event that is not listed in the protocol as an expected occurrence.

Common Toxicity Criteria Gradings

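### SAE reporting stops at six months in both stages, although RCT research procedures, including the repeated SPARC in Arm B2, run to month 36 or death

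*Protocol*

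**What the plan says.** Section 14.1.3 gives a single reporting period and does not separate the two stages: "Details of all SAEs will be documented and reported from the date of entry until the six month follow up time point".

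Section 14.1.1 limits what is reported to SAEs "that are thought to be attributable to the SPECIAL protocol (i.e. related) and are thought to be unexpected only". Section 14.1.2 adds: "No SAEs are expected to occur as a result of participation in the SPECIAL trial". Appendix 11 defines a related event as "An event which resulted from the administration of any of the research procedures".

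RCT follow-up is much longer than six months. Section 3.2 states: "Patients will be entered into the trial over a three year period and will be followed up for three years or until death". After the monthly phase, Table 2 in Section 7.2.2 schedules visits "2-monthly for 6 months then 3 monthly until death or further two years", and Section 7.2.2.3 has matching text: "Thereafter patients will be followed up three monthly until death or for a maximum of two years". At these long-term visits patients complete a questionnaire booklet and carers complete theirs. Arm B2 also repeats SPARC, with a copy going to the palliative care team each time. Patients treated for relapse or progression return to monthly assessments.

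**The concern.** Six months is the natural limit for the feasibility study, because its follow-up ends there. Applied to the RCT, the same limit closes the SAE channel while the trial is still carrying out research procedures, one of which (SPARC in Arm B2) is a randomised intervention. Relatedness is tied to any research procedure, so an event can meet every condition for reporting except its date.

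At stake is the route such an event should take: independent causality and expectedness assessment by a Clinical Coordinator (Section 14.2.3), a report to the Research Ethics Committee within 15 days (Section 14.3.1), and notice to the principal investigators (Section 14.4). The protocol does ask about harm: Section 2.1.1 raises adverse consequences of early referral, with patient anxiety as its example. Two other sources on psychological harm also thin out near month 6. HADS is not in the longer-term booklet (Appendix 8, Table 3), and the qualitative interviews are held at about three and six months (Section 7.2.3).

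**Working it through.** **Tracing a late event through the text.** Take an SAE at month 7 in Arm B2 that the investigator attributes to a SPARC assessment.

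- Related under Appendix 11: yes, it arose from a research procedure.
- Unexpected: yes, because Section 14.1.2 lists no expected SAEs.
- Inside the period in Section 14.1.3: no.
- Caught elsewhere: Section 14.2.2 covers follow-up of events already reported, not new ones. Section 7.2.2.3 collects survival, progression and resource use on the CRF, but does not reopen SAE reporting, even for patients who resume monthly visits.

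**How much follow-up lies after the cut-off.** The protocol gives no such figure, so it is derived here.

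Inputs:
- Exponential survival with median 6 months (Section 19.2.5.1); 6.5 months as the alternative (Section 1.1).
- Reporting window 0 to 6 months (Section 14.1.3).
- Follow-up cap T = 6 + 6 + 24 = 36 months (Table 2, agreeing with Section 3.2). T = 24 applies if the two-year maximum in Section 7.2.2.3 is read as a total.
- Minimum sample size 525 (Section 19.2.5).

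Formulas: S(t) = 0.5^(t/median). Mean time under follow-up to T is RM(T) = (1 − S(T))/λ, with λ = ln 2/median. Share after month 6 = 1 − RM(6)/RM(T).

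1. Check of the survival model: S(3) = 0.5^(3/6) = 70.7%, against 70% in Section 19.2.5.1. It reproduces.
2. Alive when reporting stops: S(6) = 50.0% at median 6, about 262 of 525; 52.7% at median 6.5.
3. Median 6, T = 36: λ = 0.1155; RM(36) = (1 − 1/64)/0.1155 = 8.52 months; RM(6) = 0.5/0.1155 = 4.33 months. Share after = 1 − 4.33/8.52 = 49.2%. For 525 patients: 372.8 patient-years in total, 189.4 inside the window, 183.4 after it.
4. Other readings the document allows:

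| Follow-up assumption | Median 6 | Median 6.5 |
|---|---|---|
| T = 36 for every patient | 49.2% | 51.7% |
| T = 24 for every patient | 46.7% | 48.8% |
| Common close 24 months after last entry | 48.9% | 51.3% |
| Common close 12 months after last entry | 46.7% | 49.0% |
| Common close 6 months after last entry | 43.2% | 45.3% |

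The common-close rows assume uniform accrual over 36 months, with each patient capped at 36 months. They are needed because the Trial Synopsis allows five years for both stages. Three years of RCT accrual leave at most 60 − 36 = 24 months for everything else, so late entrants may not reach month 36.

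5. Sensitivity outside the protocol's figures (assumed medians, T = 36): median 4 months gives 35%, median 8 months gives 58%.

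**The case against.** The strongest case on the other side is that this is a design choice. No other section sets a different SAE period, so nothing is contradicted. The window covers the whole monthly phase and both co-primary time points, and the main intervention, referral, takes place immediately after randomisation. Only related and unexpected SAEs count, and none are expected. Events linked to cancer treatment are excluded even within the window, and Appendix 11 leaves out deaths from the lung cancer or its treatment. Much is still recorded after month 6: survival, progression and resource use (Section 7.2.2.3), date, cause and place of death (Section 7.2.4), and hospital admissions (Section 14.1.1). SPARC forms go to the palliative care team, sites report SAEs to their own Trust (Section 14.2.1), and the DMC can hold an emergency safety meeting (Section 20.5).

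Most of this stands, and it limits the point. A reader might infer from the patient-time share that about half of the trial's safety information is lost. The document does not support that: patient-time is a poor proxy for so rare a class of event, and other data continue. A reader might also infer that the Arm B1 versus B2 comparison is biased. It is not biased by this rule: the cut-off is the same in every arm, SAEs are not a listed outcome, and Section 19.2.2.2 sets out no comparative SAE analysis.

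What does not stand is the inference that the channel can therefore close. None of the continuing data streams provides central causality review or triggers a report to the ethics committee. Because no SAE is expected, any related SAE is by definition of the class that Section 14.3.1 sends to that committee. The protocol gives no reason for stopping while its procedures go on.

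**Conclusion.** The point holds as a gap in SAE reporting, and the remedy is a cheap improvement. In the RCT, a related and unexpected SAE that arises from trial procedures after month 6 falls outside central review and onward reporting.

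About half of the patients are alive when reporting stops, and roughly 43% to 52% of follow-up time comes later. These are model-based expectations. They rest on exponential survival, a median of 6 or 6.5 months and the follow-up caps shown, with uniform accrual assumed for the lower end. They describe exposure to continuing procedures, not a number of missed events, which is likely to be small. Both co-primary outcomes fall within six months, so the efficacy conclusions are unaffected.

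**What to change.** Split Section 14.1.3 by stage. For the feasibility study, keep reporting from entry to the six-month follow-up. For the RCT, set the period for related and unexpected SAEs from randomisation to the patient's last trial visit, death or withdrawal from all follow-up, whichever comes first. In the same edit, replace the reference to all SAEs with the class defined in Section 14.1.1, since the two do not match as written. If six months is intended for the RCT, state the reason instead.

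The cost is a short text change and a slightly longer reporting duty for sites, at visits they already hold. The restriction in Section 14.1.1 keeps the added workload small.

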14.2 Reporting Procedure

14.2.1 Serious Adverse Events

For more detailed instructions on SAE reporting refer to the SAE Form Completion Guidelines contained in the ISF.

AEs defined as serious (and which are related and thought to be unexpected) require reporting as an SAE should be reported on an SAE Form. When completing the form, the investigator will be asked to define the causality and the severity of the AE which should be documented using the Common Terminology Criteria for Adverse Events (CTCAE) version 4.0 (see Appendix 11).

On becoming aware that a patient has experienced an SAE, the investigator (or delegate) must complete, date and sign an SAE Form. The form should be faxed together with a SAE Fax Cover Sheet to the Trial Office using one of the numbers listed below as soon as possible and no later than 24 hours after first becoming aware of the event:

To report an SAE, fax the SAE Form with an SAE Fax Cover Sheet to: [name] or [name]

Page | 24 of 64 Version 1.0a, 8 Apr 2016

On receipt the Trial Office will allocate each SAE a unique reference number. This number will be transcribed onto the SAE Fax Cover Sheet which will then be faxed back to the site as proof of receipt. If confirmation of receipt is not received within 1 working day please contact the Trial Office. The SAE reference number should be quoted on all correspondence and follow-up reports regarding the SAE. The SAE Fax Cover Sheet completed by the Trial Office should be filed with the SAE Form in the ISF.

For SAE Forms completed by someone other than the investigator the investigator will be required to countersign the original SAE Form to confirm agreement with the causality and severity assessments. The form should then be returned to the Trial Office in the post and a copy kept in the ISF.

Investigators should also report SAEs to their own Trust in accordance with local practice.

14.2.2 Provision of Follow-up Information

Patients should be followed up until resolution or stabilisation of the event. Follow-up information should be provided on a new SAE Form (refer to the SAE Form Completion Guidelines for further information).

14.2.3 Trial Office

On receipt of an SAE Form seriousness and causality will be determined independently by a Clinical Coordinator. An SAE judged by the investigator or Clinical Coordinator to have a reasonable causal relationship with the trial protocol will be regarded as a related SAE. The Clinical Coordinator will also assess all related SAEs for expectedness. If the event is unexpected (i.e. is not defined in the protocol as an expected event) it will be classified as an unexpected and related SAE.

14.3 Reporting to the Research Ethics Committee

14.3.1 Unexpected and Related Serious Adverse Events

The Trial Office will report all events categorised as Unexpected and Related SAEs to the Research Ethics Committee (REC) within 15 days.

14.4 Reporting to the Principal Investigators

The Trial Office will report all Unexpected and Related SAEs to Principal Investigators.

15 DATA HANDLING AND RECORD KEEPING

15.1 Data Collection

CRFs must be completed, signed/dated and returned to the Trial Office by the investigator or an authorised member of the site research team (as delegated on the Site Signature and Delegation Log) within the specified time frame. The exception to this is the Withdrawal Form which must be co-signed by the investigator. Entries on the CRF should be made in ballpoint pen, in blue or black ink, and must be legible. Any errors should be crossed out with a single stroke, the correction inserted and the change initialled and dated. If it is not obvious why a change has been made, an explanation should be written next to the change.

Page | 25 of 64 Version 1.0a, 8 Apr 2016

Data reported on each form should be consistent with the source data or the discrepancies should be explained. If information is not known, this must be clearly indicated on the form. All missing and ambiguous data will be queried. All sections are to be completed before returning.

Quality of Life, health economic and patient/carer reported data will be completed on paper forms by the participants and will be regarded as source data for the purposes of this trial. These questionnaires will be returned to the Trial Office and a copy will not be retained at site. Please note this does not include the SPARC.

In all cases it remains the responsibility of the investigator to ensure that the CRF has been completed correctly and that the data are accurate.

The completed originals should be sent to the Trial Office and a copy filed in the ISF. Trial forms may be amended by the Trial Office, as appropriate, throughout the duration of the trial. Whilst this will not constitute a protocol amendment, new versions of the form must be implemented by participating sites immediately on receipt.

The investigator should supply the Trial Office with any required source data (anonymised) on request.

16 ARCHIVING

It is the responsibility of the Principal Investigator to ensure that all essential trial documentation and source records (e.g. signed Informed Consent Forms, ISF, patients' medical records, copies of CRFs, etc.) at their site are securely retained for at least 5 years after the end of the trial. Do not destroy any documents without prior approval from the CRCTU Document Storage Manager.

17 QUALITY MANAGEMENT

The trial is being conducted under the auspices of the CRCTU according to the current guidelines for Good Clinical Practice (GCP). Participating sites will be monitored by CRCTU staff to confirm compliance with the protocol and the protection of patients' rights as detailed in the Declaration of Helsinki (Appendix 12).

17.1 Site Set-up and Initiation

All sites will be required to sign a Clinical Trial Site Agreement prior to participation. In addition all participating investigators will be asked to sign the necessary agreements including an Investigator Registration Form and supply a current *Curriculum Vitae* (CV) to the Trial Office. All members of the site research team will also be required to sign a Site Staff Registration Form and the Site Signature and Delegation Log, which should be returned to the Trial Office. Prior to commencing recruitment all sites will undergo a process of initiation. Key members of the site research team will be required to attend either a meeting or a teleconference covering aspects of the trial design, protocol procedures, AE, and collection and reporting of data and record keeping.

Page | 26 of 64 Version 1.0a, 8 Apr 2016

Sites will be provided with an ISF containing essential documentation, instructions, and other documentation required for the conduct of the trial. The Trial Office must be informed immediately of any change in the site research team.

